8.3. Exploratory Efficacy Analyses

8.3.1. Ectropion

The Ectropion Severity Score (ESS), has a maximum score of 8 points. A higher score indicates a worse ectropion. The score takes the severity of ectropion in terms of lateral and medial apposition, scleral show, conjunctival show, and roundness of the eye into account and gives an indication of the functional aspects involved in ectropion by scoring redness, excess tear film, and the position of the lacrimal punctum. The scoring is as follows in [Table 8](#).

Table 8: Ectropion Scoring

	Points per Item
--	-----------------

	0	0.5	1
Lateral apposition	Nonaffected	-	Affected
Medial apposition	Nonaffected	-	Affected
Sceral show	No	≤ 1 mm	> 1mm
Conjunctival show	No	-	Yes
Excess tear film	No	-	Yes
Redness of the eye	No	-	Yes
Round canthus	No	-	Yes
Punctum lacrimale	Invisible	Emerging	Visible
Maximum score			8 points

The observed value and change from baseline in ectropion score will be summarized descriptively by study visit and treatment group using descriptive statistics for the Double-blind Period and OLE.

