2.2.2.2. Secondary Efficacy Endpoints

The secondary efficacy endpoints of this study include the following:

- The difference in mean scores between the active trifarotene cream HE1 and vehicle groups in the following assessment indices from Baseline through Day 90:
 - 5-point Visual Index for Ichthyosis Severity (VIIS) for scaling (overall 16 points for scaling, i.e., 0-4 points for 4 body areas: chest/abdomen, back, arms, and legs)
 - Individual score for roughness (Scale: 0–4) overall
 - Palm/sole Assessment (Scale: 0–4)
 - Quality of life per Dermatology Life Quality Index (DLQI) and children’s DLQI (cDLQI)
- The difference in proportion of subjects with presence of fissures on palms/soles (presence/absence, number of fissures, and pain associated with fissures on a 0-3 scale) at Day 90 between the active trifarotene cream HE1 and vehicle groups

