2.2.2.3. Exploratory Efficacy Endpoints

The exploratory efficacy endpoints of this study include the following:

- The difference in mean ectropion (Ectropion Severity Score [ESS] of 0–8) scores between the active trifarotene cream HE1 and vehicle groups from Baseline through Day 90
- The difference in quality of life per EQ-5D-5L and EQ-5D-Y score between the active trifarotene cream HE1 and vehicle groups from Baseline through Day 90

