8.2.5. Fissures

Fissuring will be assessed by recording the presence or absence of fissures, the number of fissures present, and the pain associated with each fissure. A fissure is a longitudinal and deep crack that separates the stratum corneum and may penetrate down to the dermis, causing pain and sometimes bleeding. The subject will assess pain associated with fissures as ranging from 0-3 (none, mild, moderate, severe).

The number and proportion of subjects with fissures present on palms or soles along with 95% CIs will be summarized by treatment group and study visit. A 2-sided Pearson's Chi-Square Test, or Fisher's Exact Test, as appropriate, will be performed at the 5% significance level to determine whether there is a significant difference between treatment groups. The null hypothesis that there is no difference in proportion of subjects with fissures present between active trifarotene cream HE1 and vehicle, with a 2-sided alternative considering a difference in either direction. The difference in proportions between active trifarotene cream HE1 and vehicle (active trifarotene cream HE1 minus vehicle), 95% CIs for the differences, and *P* values for the differences in treatment will also be presented.

The number of fissures and fissure pain level will be summarized descriptively by body area and treatment group.

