8.3.2. Quality of Life per EQ-5D-5L and EQ-5D-Y

The EQ-5D is a measure of health related quality of life. The EQ-5D consists of a descriptive system and the EQ visual analog scale (VAS). The EQ-5D-5L is intended for use in adult subjects, while the EQ-5D-Y is to be used for children and adolescents. The investigator will use his or her judgment of the maturity of the subject to decide which version of the EQ-5D to use; the same version will be used for the subject throughout the study. The descriptive system comprises 5 dimensions: mobility, self-care, usual activities, pain/discomfort, and anxiety/depression. The EQ VAS records the subject’s self-rated health on a vertical 0-100 VAS. This can be used as a quantitative measure of health outcome that reflects the subject’s own judgement.

The observed value and change from baseline in EQ-5D-5L/EQ-5D-Y score will be summarized descriptively by study visit and treatment group using descriptive statistics for the Double-blind Period and OLE.

9. Safety and Tolerability Analysis

Safety variables include treatment-emergent AEs, clinical laboratory values, vital signs, ECG readings, local tolerability assessments, and physical examination results. No formal inferential analyses will be conducted for safety variables in either period.

Safety analyses through Day 90 of the Double-blind Period will be conducted using data from the Safety population and safety analyses in the OLE will be conducted using the OLE Safety population.

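### Ectropion and EQ-5D are defined as active-versus-vehicle differences, but the plan provides only per-arm summaries and no between-arm estimate or confidence interval

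*SAP*

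**What the plan says.** **Endpoint definitions.** SAP Section 2.2.2.3 lists two exploratory efficacy endpoints. The first is "The difference in mean ectropion (Ectropion Severity Score [ESS] of 0–8) scores between the active trifarotene cream HE1 and vehicle groups"; it covers the same double-blind time frame as the second. The second is "The difference in quality of life per EQ-5D-5L and EQ-5D-Y score between the active trifarotene cream HE1 and vehicle groups from Baseline through Day 90".

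**Planned analyses.** Section 8.3.1 on ectropion: "The observed value and change from baseline in ectropion score will be summarized descriptively by study visit and treatment group using descriptive statistics". Section 8.3.2 on EQ-5D: "The observed value and change from baseline in EQ-5D-5L/EQ-5D-Y score will be summarized descriptively by study visit and treatment group". Neither section names a model, a difference, a confidence interval or a P value.

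**Table shells.** Table 14.2.7.1 (ectropion) shows n, mean (SD), median and range for observed value and change from baseline, repeated for the pooled active and vehicle columns. Tables 14.2.8.1 (EQ-5D-5L) and 14.2.8.2 (EQ-5D-Y) reuse that shell for each dimension and for the self-rated health scale. None has a row comparing an active arm with vehicle.

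**Fissures.** Section 2.2.2.2 words the secondary endpoint as "The difference in proportion of subjects with presence of fissures on palms/soles (presence/absence, number of fissures, and pain associated with fissures". The comparison is active against vehicle at the last double-blind visit, and pain is scored 0 to 3. Section 8.2.5 tests and estimates fissure presence against vehicle. For the rest it says "The number of fissures and fissure pain level will be summarized descriptively by body area and treatment group".

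**The concern.** An endpoint worded as a between-group difference needs an analysis that estimates the difference. Here the SAP names the contrast and then plans only what is needed to describe each arm. The difference and its interval, which answer the question asked, are left for the reader to assemble.

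Timing adds to this. Section 1 says the SAP will be filed before any unblinded analysis and that analyses outside it will be identified as post hoc in the study report. If the comparison is not added now, the contrast that defines these two endpoints can be reported only under that label, although it is written into the endpoint list.

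**Working it through.** **1. Is the omission specific to these endpoints?** The definitions, methods and shells line up as follows.

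| Item | Defined as a difference from vehicle? | Difference and CI planned? |
|---|---|---|
| VIIS, roughness, palm/sole, DLQI/cDLQI | Yes (2.2.2.2) | Yes (8.2.1 to 8.2.4; shell 14.2.1.6.1) |
| Fissure presence | Yes (2.2.2.2) | Yes (8.2.5; shell 14.2.6.1.1) |
| Ectropion | Yes (2.2.2.3) | No (8.3.1; shell 14.2.7.1) |
| EQ-5D | Yes (2.2.2.3) | No (8.3.2; shells 14.2.8.1 and 14.2.8.2) |
| Fissure number and pain | Named only in a parenthesis (2.2.2.2) | No (8.2.5; shell 14.2.6.2.1) |

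**2. Does the SAP declare these items descriptive by design?** Section 8 limits formal inference in the open-label extension, and Section 9 rules it out for safety. Neither covers double-blind ectropion or EQ-5D. Section 6.1.3 says P values for secondary and exploratory endpoints will be given for information, yet ectropion and EQ-5D are the only exploratory efficacy endpoints in Section 2.2.2.3 and no P value is planned for either. Section 10 lists one change from the planned analysis, the added age factor. The mismatch is therefore not explained anywhere in the document.

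**3. How precise would the missing estimate be?** The SAP gives no precision figure to reproduce for these endpoints, and no SD, so results are in units of the SD of the variable compared.

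Inputs: 65 enrolled (Section 1); 1:1:1 allocation and 20% loss (Section 3, sample size paragraph); two-sided 0.05 (Section 4.1). If allocation stayed equal, 65/3 = 21.7 per arm; after an assumed 20% loss, 0.8 × 21.7 = 17.3.

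Half-width of the 95% CI for a difference of two means = t(0.975, 2n − 2) × √(2/n):

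- n = 17: 2.037 × 0.343 = 0.70 SD
- n = 21: 2.021 × 0.309 = 0.62 SD
- n = 32 (planned evaluable per arm): 1.999 × 0.250 = 0.50 SD

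**4. What would baseline adjustment add?** The shells already show change from baseline, so change scores are the right comparator. With equal variances at both times and baseline-to-Day-90 correlation ρ, the variance of change is 2σ²(1 − ρ) and the baseline-adjusted residual variance is σ²(1 − ρ²). The standard-error ratio is √[(1 − ρ²) / (2(1 − ρ))] = √[(1 + ρ)/2].

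- ρ = 0.5: √0.75 = 0.866, a 13% reduction
- ρ = 0.7: √0.85 = 0.922, an 8% reduction

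The correlations are assumptions. At 21 per arm the half-width in change-score SDs would fall from 0.624 to between 0.624 × 0.866 = 0.54 and 0.624 × 0.922 = 0.58.

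**5. Can an existing model be reused?** Table 1 schedules ectropion, EQ-5D and VIIS at the same post-baseline double-blind visits (Days 14, 30, 60 and 90), so the Section 8.2.1 MMRM fits that structure. For EQ-5D, the adult and youth versions are tabulated separately and age group is close to constant within each, so that factor should be dropped. Section 8.2.4 already does this for DLQI/cDLQI.

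**The case against.** The main objection is that descriptive reporting of exploratory endpoints is a legitimate choice in a Phase 2 trial stopped at 65 subjects with no multiplicity control, and that intervals of ±0.6 to ±0.7 SD will settle little. This stands as a reason for low severity. It does not remove the inconsistency, because the SAP does not say that it made that choice.

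Several stronger readings are tempting but unsupported:

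- *That the reader is left with no measure of uncertainty.* Per-arm n and SD are shown for observed value and change, and Section 4.1 adds the standard error to continuous summaries. An unadjusted difference and interval can be computed from these.
- *That baseline adjustment would gain up to 29%.* That figure is 1 − √(1 − 0.7²), which compares adjustment with raw Day 90 means. For ectropion and EQ-5D the plan reports change, and the gain at ρ = 0.7 is 8%.
- *That fissure number and pain are separately defined difference endpoints.* They appear only in a parenthesis that matches the assessment footnote in Table 1. The endpoint itself is a difference in the proportion with fissures present, which is fully compared with vehicle. A count and a 0-3 score cannot be that proportion. The wording is loose, but no defined comparison has been dropped.
- *That entry criteria invite ectropion imbalance.* The IGA excludes palms and soles, but this says nothing about eyelids, and the full eligibility criteria are not in the SAP.

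**Conclusion.** The point holds for ectropion and EQ-5D: both are defined as active-versus-vehicle differences, and neither the text nor the shells plan an estimate of that difference. For fissure number and pain the point reduces to ambiguous wording in Section 2.2.2.2.

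Severity is low. The primary analysis, alpha, power and safety conclusions are unaffected. What is lost is a planned, baseline-adjusted estimate with an interval of roughly ±0.62 SD at 21 per arm, or ±0.70 SD at 17, before any gain from adjustment. These figures assume equal allocation of the 65 enrolled and, for 17, a 20% loss. The 8% to 13% gain assumes correlations of 0.7 to 0.5 and equal variances. Without SDs in the document, none of this can be converted to scale points.

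**What to change.** - **Section 8.3.1:** add Day 90 LS mean differences (each active arm minus vehicle) with 95% CIs for the ectropion total score, from the VIIS MMRM with baseline, treatment, visit, treatment-by-visit and age group.
- **Section 8.3.2:** add the same for the EQ VAS, separately for EQ-5D-5L and EQ-5D-Y and without age group, following the DLQI/cDLQI model. If EQ-5D-Y is too sparse to fit, give the unadjusted difference in change with its 95% CI.
- **Tables 14.2.7.1, 14.2.8.1 and 14.2.8.2:** add rows comparing each active arm with vehicle, labelled informational in line with Section 6.1.3.
- **Fissures:** either add a simple Day 90 difference with 95% CI for fissure number in Section 8.2.5 and Table 14.2.6.2.1, or reword Section 2.2.2.2 to say that number and pain are descriptive.

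If the sponsor prefers to keep ectropion and EQ-5D descriptive, Sections 2.2.2.3 and 6.1.3 should say so; that removes the contradiction but leaves the contrast unestimated.

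The cost is a few model calls reusing existing code and some table rows. The downside is a few more imprecise exploratory intervals without multiplicity adjustment.

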8.3.2. Quality of Life per EQ-5D-5L and EQ-5D-Y

The EQ-5D is a measure of health related quality of life. The EQ-5D consists of a descriptive system and the EQ visual analog scale (VAS). The EQ-5D-5L is intended for use in adult subjects, while the EQ-5D-Y is to be used for children and adolescents. The investigator will use his or her judgment of the maturity of the subject to decide which version of the EQ-5D to use; the same version will be used for the subject throughout the study. The descriptive system comprises 5 dimensions: mobility, self-care, usual activities, pain/discomfort, and anxiety/depression. The EQ VAS records the subject’s self-rated health on a vertical 0-100 VAS. This can be used as a quantitative measure of health outcome that reflects the subject’s own judgement.

The observed value and change from baseline in EQ-5D-5L/EQ-5D-Y score will be summarized descriptively by study visit and treatment group using descriptive statistics for the Double-blind Period and OLE.

9. Safety and Tolerability Analysis

Safety variables include treatment-emergent AEs, clinical laboratory values, vital signs, ECG readings, local tolerability assessments, and physical examination results. No formal inferential analyses will be conducted for safety variables in either period.

Safety analyses through Day 90 of the Double-blind Period will be conducted using data from the Safety population and safety analyses in the OLE will be conducted using the OLE Safety population.

9.1. Adverse Events

All AEs, TEAEs, and SAEs will be coded using the MedDRA dictionary Version 21.1.

Treatment-emergent AEs are defined as:

- AEs with onset at the time of or following the start of treatment with study drug through 14 days after the last application of study drug, or
- AEs starting prior to the start of treatment but increasing in severity or relationship at the time of, or following, the start of treatment with study drug through the last application of study drug.

The causal relationship of the AE to the study drug is determined by the investigator as Not Related, Unlikely Related, Possibly Related, and Related. These will be mapped to Unrelated (Not Related or Unlikely Related) and Related (Possibly Related, or Related).

Adverse event severity grades are reported as mild, moderate, or severe.

Summaries of incidence rates (frequencies and percentages) of individual TEAEs will be presented by SOC, PT, and treatment group for the Double-blind Period and OLE. Such summaries will be displayed for all TEAEs, TEAEs by maximum severity, and TEAEs by relationship.

Each subject will be counted only once within each summation level (SOC and PT). If a subject experiences more than 1 TEAE within each summation level, the TEAE with the strongest relationship or the maximum severity, as appropriate, will be included in the summaries of relationship and severity. If a particular event is missing the severity and/or relationship, then the strongest possible severity or relationship will be assumed for analysis (severity = severe, relationship = related).

Incidences will be presented by descending frequency of SOC and PT within SOC, and then alphabetically within PT where the incidence is the same; this is based on overall subjects then alphabetically in case of a tie.

Missing and partially missing AE start and/or stop dates and times will be imputed, for the purpose of statistical analysis, according to the specifications described in Section 6.1.8.

In the AE data listings, all AEs will be displayed. AEs that are treatment emergent will be flagged.

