Upon sponsor discretion, this study was terminated before the study completed enrollment; however, all planned analyses will still occur. Sixty-five (65) subjects were enrolled in the study before termination. The statistical plan described hereafter is an *a priori* plan. It will be submitted to file prior to any unblinded inferential or descriptive analysis of data pertaining to Mayne Pharma's study 18-ICH-001.

2. Study Objectives and Endpoints

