2.1. Study Objectives

2.1.1. Primary Objective

The primary objective is to compare the safety and efficacy of 2 concentrations of trifarotene cream HE1 versus vehicle in adults and adolescents with moderate to severe autosomal recessive ichthyosis with lamellar scale, also known as lamellar ichthyosis (LI) after 90 days of treatment.

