3.1. Overall Design

This is a 2-cohort, multicenter study in subjects with moderate to severe LI (i.e., 3–4 on a 5-point Investigator’s Global Assessment [IGA] where 0 = clear; 1 = almost clear; 2 = mild; 3 = moderate; 4 = severe). Adults (Cohort A) and adults and adolescents (Cohort B) will be randomized in a double-blind fashion to 1 of 2 doses of trifarotene cream HE1 or vehicle and treated twice weekly for 90 days.

Approximately 15 adults (≥ 18 years old) will be randomized into the first cohort of subjects (Cohort A) in a 1:1:1 ratio to trifarotene cream HE1 100 $\mu\text{g/g}$, trifarotene cream HE1 200 $\mu\text{g/g}$, or vehicle and treated twice weekly for up to 90 days. After the initial 15 subjects complete at least 28 days of treatment, an independent data safety monitoring board (DSMB) will review aggregate safety and tolerability data.

If no safety issues are identified, both adults and adolescents (ages 12 to 17 years, inclusive) will be allowed to enroll in Cohort B. Subjects in Cohort B will be randomized 1:1:1 to trifarotene cream HE1 100 $\mu\text{g/g}$, trifarotene cream HE1 200 $\mu\text{g/g}$, or vehicle and treated twice weekly for up to 90 days in the same manner as subjects in Cohort A. All subjects (Cohort A and Cohort B) who complete the randomized, Double-blind Period of the study will be eligible to enter a 90-day, Open-label Extension (OLE) in which additional PK, safety, and efficacy data will be collected. Subjects in the OLE will receive open-label trifarotene cream HE1 200 $\mu\text{g/g}$ twice weekly for up to 90 days. A schematic of each period is provided in [Figure 1](#) and [Figure 2](#).

Figure 1: Double-blind Study Design

[figure not shown]
[figure not shown]

Figure 2: Open-label Study Design

The first cohort of 15 adult subjects is a reasonable sample size to assess safety and tolerability before enrolling adolescents. Accounting for a 20% drop-out/nonevaluable rate, a total sample size of 120 subjects randomized in a 1:1:1 ratio to 2 active trifarotene cream HE1 arms and a vehicle cream arm will provide >80% power to detect a difference between each separate trifarotene cream HE1 arm (32 evaluable subjects) and the vehicle cream arm (32 evaluable subjects) 2-sided Fisher's Exact Test assuming a 70% success rate and a 40% success rate, respectively. This study is not powered to detect a difference between the 2 active arms.

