4.2. Interim Analysis and Data Monitoring

The DSMB will meet after 15 subjects in Cohort A have completed at least 28 days of double-blind treatment to review aggregate safety and tolerability data (including PK concentration data, PK parameters, and ECG results). The safety data will be unblinded. At that time, the DSMB will decide whether Cohort B (adults and subjects aged 12–17) may begin enrolling, or if additional adult safety data are required before allowing subjects aged 12 – 17 to participate in the study. The DSMB will meet again after 60 subjects have enrolled in the study. The sponsor may request additional reviews, e.g., should any other findings/issues pertaining to safety emerge requiring DSMB review. Details of the DSMB operation will be developed in conjunction with the members of the DSMB before the first meeting and will be modified as required. The unblinded DSMB outputs will not be seen by anyone except the DSMB and the performing statistician.

The primary analysis period is the first 90 days of treatment (i.e., the Double-blind Period). Overall unblinding will take place at the end of the Double-blind Period of the study only after database lock has been achieved. The data will be cleaned and frozen and an unblinded analysis of the data will be performed. The data will be considered final at this point and no changes to these data will be permitted following unblinding with the exception of outcomes and end dates of ongoing AEs and concomitant mediations. A second analysis will take place for endpoints assessed from Day 90 through the OLE.

The protocol assumes a 20% dropout/non-evaluable rate. This rate will be continuously monitored throughout the COVID-19 pandemic. In the event that this rate dramatically increases, a blinded sample size reestimation may be performed to ensure statistical power for the primary endpoint is maintained using the assumptions in Section 3.2.

5. Analysis Populations

The following 5 analysis populations are planned for the Double-blind Period of this study:

- **Safety:** all subjects who are randomized to treatment and receive at least 1 application of study drug in the Double-blind Period. This population will be the primary population for analyses of safety. Subjects will be analyzed by actual treatment received.

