6.1.2. Adjustments for Covariates

If there is a statistical difference among treatment groups with respect to baseline characteristics, that variable may be added to the statistical models as a blocking factor or covariate to determine the effect on treatment. Age group and baseline score are planned for inclusion in statistical models, unless otherwise indicated. Age group will be categorized as adolescents (ages 12 to 17 years, inclusive) and adults (≥ 18 years).

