6.1.8. Data Adjustments/Handling/Conventions

All collected data will be presented in listings. Data not subject to analysis according to this plan will not appear in any tables or graphs but will be included only in the data listings.

All *P* values will be displayed in 4 decimals and rounded using standard scientific notation (e.g., 0.XXXX). If a *P* value less than 0.0001 occurs it will be shown in tables as <0.0001.

Adverse events will be coded using the MedDRA version 21.1 thesaurus. Concomitant mediations will be coded using the WHO-DD version September 2018.

A treatment-related AE is any AE with a relationship to the study drug of possibly related and related.

If partial AE or medication dates occur, the convention for replacing missing dates for the purpose of statistical analysis is as follows:

For partial AE and medication start dates:

- If the year is unknown, then do not impute the date but assign a missing value.
- If the year is known, but the month or month and day is unknown, then:
 - If the year matches the year of first dose date and the end date (if present) is after first dose date, then impute as the month and day of the first dose date.
 - Otherwise, assign 01 January.
- If the year and month are known, but the day is unknown, then:
 - If the month and year match the month and year of the first dose date, then impute as the day of the first dose date.
 - Otherwise, assign 01.

For partial AE and medication end dates:

- If the year is unknown, then do not impute the date but assign as missing value.
- If the year is known, but the month or month and day is unknown, then:
 - If the year matches the year of the last date of the study (date of last contact if subject lost to follow-up; date of completion or early termination otherwise), then impute as the month and day of the last date of the study.
 - Otherwise, assign 31 December.
- If the year and month are known, but the day is unknown, then:
 - If the month and year match the month and year of the last date of the study, then impute as the day of the last date of the study.
 - Otherwise, assign the last day of the month.

If partial times occur, the convention is as follows:

- if the missing time occurs on the day of the first dose and both the hour and minute are missing then the time assigned is the time of the first dose, otherwise if both the hour and minute are missing and the date is not the date of first dose the time assigned is 12:00;

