7.3. Demographics and Other Baseline Characteristics

Summary statistics for age, gender, race, ethnicity, height, weight, BMI, and baseline IGA score will be presented by treatment group. See Section 6.1.1 for definition of baseline.

These analyses will be conducted for the ITT and OLE ITT populations.

The number and percent of subjects reporting various medical histories, grouped by MedDRA system organ class (SOC) and preferred term (PT), will be tabulated by treatment group. This analysis will be conducted for the Safety population.

Prior medications will be summarized by treatment group, by the number and percentage of subjects taking each medication, classified using WHO-DDE ATC Class Level 4 and preferred term (ATC Class Level 5) and will be presented by treatment group and overall. This analysis will be conducted for the Safety population. Prior medications are defined in Section 9.7.

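### The PK concentration shell leaves out five scheduled all-subject sampling visits; separately, no safety or tolerability table is split by age group and no baseline row counts adolescents

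*SAP*

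**What the plan says.** **Exposure.** Section 2.2.3 names plasma concentrations of the drug and its major metabolites as the PK endpoints. Section 5 assigns the PK population to the summary of all of them. Section 11.1 has trough samples drawn from every subject at clinic visits and concentrations summarised at each time point. Table 1, footnote n, places troughs at Days 14, 60 and 90. Table 2 and its PK footnote add samples from all subjects at Days 120 and 180. The programming note under the Table 14.4.1.1 shell restricts the table to predose and six postdose times on Day 1 and Day 30.

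**Age.** The primary objective (Section 2.1.1) is to "compare the safety and efficacy of 2 concentrations of trifarotene cream HE1 versus vehicle in adults and adolescents". Section 3.1 says that the first cohort of 15 adults "is a reasonable sample size to assess safety and tolerability before enrolling adolescents". Section 6.1.2 defines the variable: "Age group will be categorized as adolescents (ages 12 to 17 years, inclusive) and adults". It is then used in the efficacy models only. For adverse events, Section 9.1 states: "Summaries of incidence rates (frequencies and percentages) of individual TEAEs will be presented by SOC, PT, and treatment group". For baseline, Section 7.3 states: "Summary statistics for age, gender, race, ethnicity, height, weight, BMI, and baseline IGA score will be presented by treatment group". On numbers, Section 1 gives only the total: "Sixty-five (65) subjects were enrolled in the study before termination".

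**The concern.** The two points have different standing.

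The PK shell does not match the text it should carry out. Systemic exposure is a secondary objective, and serial sampling is an optional substudy. The visit samples are therefore the only exposure data planned for everyone. A programmer who follows the shell leaves most of them out of the report's tables.

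The age point is about usefulness. The design holds adolescents back until adult safety, tolerability, PK and ECG data have been reviewed, and then plans to report adolescent safety only pooled with adults. Followed as written, the report has no tabulated adolescent TEAE rate or tolerability distribution. Its baseline table does not show how many adolescents the pooled figures rest on.

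**Working it through.** **1. PK visits: planned against tabulated**

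- On-treatment visits with a sample from all subjects, double-blind (Table 1): Days 14, 30, 60, 90 = 4.
- The same in the extension (Table 2): Days 120, 180 = 2. Total 4 + 2 = 6.
- In the Table 14.4.1.1 shell: Day 30 only.
- Absent: 3 of 4 double-blind visits, 5 of 6 overall.
- The shell has 7 times x 2 days = 14 blocks. Of these, 6 postdose times x 2 days = 12 come from substudy subjects only. A subject outside the substudy can contribute to two blocks, Day 1 predose and Day 30 predose, so to one on-treatment value. This assumes that the ordinary Day 30 sample is placed in the predose block.
- Table 12 plans one concentration table and one parameter table. The missing visits are not summarised anywhere else.

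**2. Age group: where it appears**

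- Sections 9.1 to 9.7 group safety results by treatment, visit, body area, period, severity or relationship. None uses age group.
- Table 11 titles and the 14.3.x shells: 0 with an age split. The columns are the treatment arms and pooled totals.
- Table 14.1.2.1: age as n, mean (SD), median and range; 0 age-category rows.
- Listing 16.2.4.1 gives each subject's age under a randomized-treatment header. Listings 16.2.7.1 (AEs) and 16.2.9.3 (tolerability) have no age column.

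**3. How many adolescents?** Total 65 and about 15 Cohort A adults give at most 65 - 15 = about 50. The lower bound is 0. The SAP narrows it no further.

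**4. What a by-age table could show.** With 0 events in n subjects, the one-sided 95% upper limit is 1 - 0.05^(1/n). The values of n are assumptions:

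| Adolescents in a cell | Upper limit after 0 events |
|---|---|
| 3 | 63.2% |
| 7 | 34.8% |
| 14 | 19.3% |

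**5. Size of the tolerability table.** Section 9.5 names five areas (chest/abdomen, back, arms, legs, face/neck). The Table 14.3.6.3.1 shell shows chest/abdomen and continues for back, arms and legs, so it has four. As in the shell: 4 areas x 3 signs x 5 visits = 60 blocks. As Section 9.5 requires: 5 x 3 x 5 = 75 blocks per age group.

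**The case against.** **On PK.** The sentence in Section 11.1 about summarising at each time point opens with noncompartmental analysis, so it could be read as meaning the serial substudy times only. The values are also not lost: Section 6.1.8 says "All collected data will be presented in listings", and Listing 16.2.5.4.3 covers concentrations. The second part stands. The first does not rescue the shell, because Section 5 has all PK endpoints summarised, Section 2.2.3 defines them as plasma concentrations without limiting them to the substudy, and the table's own title is by study visit.

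**On age.** Most of the opposing case stands.

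- A reader might infer that the SAP breaks a commitment to report adolescent safety separately. It makes none. The primary objective names adolescents as part of the population in a comparison with vehicle, and the secondary exposure objective names no age group. Section 9 is consistent with itself.
- A reader might infer that the number of adolescents per arm cannot be known. It can be counted from Listing 16.2.4.1, and AE detail can be matched by subject ID for at most 65 enrolled subjects. Section 1 also allows labelled post-hoc analyses.
- A reader might infer that pooling hides an adolescent signal of some given size. The documents do not support any size, because neither adolescent numbers nor rates are stated.
- Safety review did not stop at the adult data: the DSMB meets again after 60 subjects enrol, and the sponsor may ask for more reviews. But Section 4.2 says "The unblinded DSMB outputs will not be seen by anyone except the DSMB and the performing statistician", so this puts nothing in the report.

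The cDLQI and EQ-5D-Y tables come close to adolescent-only results. They cover quality of life, the version is chosen by investigator judgement, and the cDLQI is meant for ages 12 to 16, so neither counts the 12-to-17 group.

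**Conclusion.** Both points are minor.

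(1) The Table 14.4.1.1 shell is wrong against the SAP's own text. It omits Days 14, 60, 90, 120 and 180, five of the six on-treatment visits at which every subject in the period is sampled. This is a mismatch for all ages and does not depend on the age point.

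(2) The lack of an age-group count row and of any by-age safety or tolerability table is a reasonable thing to improve, given the primary objective and the gated entry of adolescents. It is neither a contradiction nor a broken promise. Its effect on pooled rates cannot be sized, because the number of adolescents is known only to lie between 0 and about 50. If few enrolled, the by-age tables will say little beyond the listings; the count row would at least make that visible.

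**What to change.** **PK.** Add Days 14, 60 and 90 to Table 14.4.1.1. Add Days 120 and 180 as an extension block under a single 200 µg/g column, since every extension subject, including those first given vehicle, receives that strength. Cost: five visits in one shell.

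**Baseline.** Add an age-group row (12 to 17; 18 and over) to Table 14.1.2.1. Table 14.1.2.2 uses the same shell and inherits it. The variable already exists.

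**Tolerability shell.** Restore face/neck before anything is repeated by age. The extension shell should also gain Day 180, which Table 2 schedules.

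**By-age repeats.** Run the TEAE overview (14.3.1.1.1 and 14.3.1.1.2) and local tolerability (14.3.6.3.1 and 14.3.6.3.2) by age group within treatment, descriptively and without tests: 4 tables x 2 age groups = 8 runs. State in Section 9 that they are descriptive. The price is sparse cells, with tolerability the longest at 75 double-blind blocks per age group. If pages are limited, the count row and the TEAE overview come first.

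**Optional.** By-age SOC/PT and PK tables, and an age column in Listings 16.2.7.1, 16.2.9.3 and 16.2.5.4.3.

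Sample size, alpha and models do not change. Made before unblinding, the additions are prespecified; made later, they would have to be labelled post hoc.
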